#### 7.2.1.7. Visit 6 (Week 28 $\pm$ 1)

- Every effort should be made to remind the subject of dosing requirements for PK sampling ([Section 5.1](#)) 1-3 days prior to the scheduled visit
- Patient-reported efficacy assessments
  - PtGA
  - HAQ-DI
  - SF-36
  - PROMIS-29 Short Form
  - Patient VAS score for pain

- FACIT-Fatigue Score
- 5-D Itch Questionnaire
- Skindex-29+3
- EQ-5D questionnaire
- Patient Improvement Questionnaire for Subjects (see [Appendix 4](#))
- Collect and count capsules of returned study product
- Record concomitant medication(s)
- AE monitoring
- Contraceptive assessment and record of LMP for WOCBP
- Vital signs (including BP, pulse rate, respiratory rate, and temperature) and weight
- 12 lead ECG
- Spirometry
- Brief physical examination
- Physician assessments of efficacy
  - MMT-8
  - CDASI score
  - IGA scale of skin activity
  - EMGA (10-cm VAS)
  - MDGA (10-cm VAS and Likert Scale)
- Patient Improvement Questionnaire for Physicians (see [Appendix 3](#))
- Laboratory tests
  - CBC with differential cell count and platelets
  - Metabolic panel (includes ALT, AST, and LDH)
  - CK and aldolase
  - Blood biomarkers
  - Blood for flow cytometry (optional at selected sites)
  - Urine dipstick
  - Urine  $\beta$ hCG in WOCBP
- Lenabasum plasma concentration and metabolite profiling
- Dispense study product

### 7.2.1.8. Visit 8 (Week 40 ± 1)

- Patient-reported efficacy assessments
  - PtGA
    - HAQ-DI
    - SF-36
  - PROMIS-29 Short Form
    - Patient VAS score for pain
    - FACIT-Fatigue Score
  - 5-D Itch Questionnaire
    - Skindex-29+3
    - EQ-5D questionnaire
- Collect and count capsules of returned study product
- Record concomitant medication(s)
- AE monitoring
- Contraceptive assessment and record of LMP for WOCBP
- Vital signs (including BP, pulse rate, respiratory rate, and temperature) and weight
- Brief physical examination
- Physician assessments of efficacy
  - MMT-8
  - CDASI score
    - IGA scale of skin activity
    - EMGA (10-cm VAS)
    - MDGA (10-cm VAS and Likert Scale)
- Laboratory tests
  - CBC with differential cell count and platelets
  - Metabolic panel (includes ALT, AST, and LDH)
  - CK and aldolase
  - Urine  $\beta$ hCG in WOCBP
- Dispense study product

#### 7.2.1.9. Visit 10^2 (Week 52 ± 1) or Early Termination (ET)

- Every effort should be made to remind the subject of dosing requirements for PK sampling ([Section 5.1](#)) 1-3 days prior to the scheduled visit
- Patient-reported efficacy assessments
  - PtGA
  - HAQ-DI
  - SF-36
  - PROMIS-29 Short Form
  - Patient VAS score for pain
  - FACIT-Fatigue Score
  - 5-D Itch Questionnaire
  - Skindex-29+3
  - EQ-5D questionnaire
- Patient Improvement Questionnaire for Subjects (see [Appendix 4](#))
- Collect and count capsules of returned study product
- Record concomitant medication(s)
- AE monitoring
- Contraceptive assessment and record of LMP for WOCBP
- Vital signs (including BP, pulse rate, respiratory rate, and temperature) and weight
- 12 lead ECG
- Spirometry
- Full physical examination
- Physician assessments of efficacy
  - MMT-8
  - CDASI score
  - IGA scale of skin activity
  - EMGA (10-cm VAS)
  - MDGA (10-cm VAS and Likert Scale)
- Patient Improvement Questionnaire for Physicians (see [Appendix 3](#))
- Laboratory tests

---

 For subjects who rollover into the OLE, data collected at Part A, Visit 10, will also be used for Part B, Visit B1.

- CBC with differential cell count and platelets
- Metabolic panel (includes ALT, AST, and LDH)
- CK and aldolase
- Blood biomarkers
- Blood for flow cytometry (optional at selected sites)
- Paxgene tube collection
- Autoantibody measurements
- Urine  $\beta$ hCG in WOCBP
- Urine dipstick
- Skin biopsies (optional at selected sites)
- Skin photography (optional at selected sites)
- Lenabasum plasma concentration and metabolite profiling
- Informed Consent for Part B

## 7.2.2. Part B

### 7.2.2.1. Visit B1 (Day B1)

- For subjects who rollover into the OLE, data collected at Part A, Visit 10 (see [Section 7.2.1.9](#)), will also be used for Part B, Visit B1.
- Informed Consent for Part B
- Dispense study product

### 7.2.2.2. Visit B2, Visit B4, and Visit B6 (Weeks 4, 20, and 36)

- Patient-reported efficacy assessments
  - PtGA
  - HAQ-DI
  - SF-36
  - PROMIS-29 Short Form
  - Patient VAS score for pain
  - FACIT-Fatigue Score
  - 5-D Itch Questionnaire
  - Skindex-29+3

---

 Subjects who rollover into Part B should sign an ICF by Visit 10 in Part A and preferably earlier than Visit 10, if possible.

- EQ-5D questionnaire
- Collect and count capsules of returned study product
- Record concomitant medication(s)
- AE monitoring
- Contraceptive assessment and record of LMP for WOCBP
- Vital signs (including BP, pulse rate, respiratory rate, and temperature) and weight
- Spirometry
- Brief physical examination
- Physician assessments of efficacy
  - MMT-8
  - CDASI score
  - IGA scale of skin activity
  - EMGA (10-cm VAS)
  - MDGA (10-cm VAS and Likert Scale)
- Laboratory tests
  - CBC with differential cell count and platelets
  - Metabolic panel (includes ALT, AST, and LDH)
  - CK and aldolase
  - Urine  $\beta$ hCG in WOCBP
  - Urine dipstick
- Dispense study product

#### **7.2.2.3. Visit B3, Visit B5, and Visit B7 (Weeks 12, 28, and 44)**

- Patient-reported efficacy assessments
  - PtGA
  - HAQ-DI
  - SF-36
  - PROMIS-29 Short Form
  - Patient VAS score for pain
  - FACIT-Fatigue Score
  - 5-D Itch Questionnaire
  - Skindex-29+3

- EQ-5D questionnaire
- Collect and count capsules of returned study product
- Record concomitant medication(s)
- AE monitoring
- Contraceptive assessment and record of LMP for WOCBP
- Vital signs (including BP, pulse rate, respiratory rate, and temperature) and weight
- Brief physical examination
- Physician assessments of efficacy
  - MMT-8
  - CDASI score
  - IGA scale of skin activity
  - EMGA (10-cm VAS)
  - MDGA (10-cm VAS and Likert Scale)
- Dispense study product

#### **Additional Procedures for Visit B5 ONLY**

- 12 lead ECG
- Blood Biomarkers

#### **7.2.2.4. Visit B8 (Week 52) or Early Termination (ET)**

- Patient-reported efficacy assessments
  - PtGA
  - HAQ-DI
  - SF-36
  - PROMIS-29 Short Form
  - Patient VAS score for pain
  - FACIT-Fatigue Score
  - 5-D Itch Questionnaire
  - Skindex-29+3
  - EQ-5D questionnaire
- Collect and count capsules of returned study product
- Record concomitant medication(s)
- AE monitoring

- Contraceptive assessment and record of LMP for WOCBP
- Vital signs (including BP, pulse rate, respiratory rate, and temperature) and weight
- 12 lead ECG
- Spirometry
- Full physical examination
- Physician assessments of efficacy
  - MMT-8
  - CDASI score
  - IGA scale of skin activity
  - EMGA (10-cm VAS)
  - MDGA (10-cm VAS and Likert Scale)
- Laboratory tests
  - CBC with differential cell count and platelets
  - Metabolic panel (includes ALT, AST, and LDH)
  - CK and aldolase
  - Urine  $\beta$ hCG in WOCBP
  - Urine dipstick
  - Blood biomarkers
  - Autoantibody measurements

### **7.2.3. Safety Follow-up (4 $\pm$ 1 Weeks after last visit)**

**Part A:** The Safety Follow-up Visit is to occur 4 $\pm$ 1 weeks after the last visit (Visit 10/ET) and is to be completed by subjects who do not rollover into Part B.

**Part B:** The Safety Follow-up Visit is to occur 4  $\pm$  1 weeks after the last visit (Visit B8 or Visit C8 if OLE is extended). Subjects who discontinue at any stage and for any reason will be encouraged to complete the Safety Follow-up Visit 4  $\pm$  1 weeks after the ET Visit.

#### **Procedures for Safety Follow-up include:**

- Record concomitant medication(s)
- AE monitoring
- Contraceptive assessment and record of LMP for WOCBP
- Vital signs (including BP, pulse rate, respiratory rate, and temperature) and weight
- Brief physical examination
- Laboratory tests

- CBC with differential cell count and platelets
- Metabolic panel (includes ALT, AST and LDH)
- Urine  $\beta$ hCG in WOCBP

#### **7.2.4. Unscheduled Visit**

Unscheduled visits may be necessary to assess the subject for safety purposes. In this case, the following evaluations should be obtained, at a minimum:

- AE monitoring
- Record concomitant medications
- Vital signs
- Medical history as relevant to the reason for the unscheduled visit
- Physical examination as relevant to the reason for the unscheduled visit
- Laboratory tests as relevant to the reason for the unscheduled visit

#### **7.2.5. End of Study**

End of Study is defined as the date of Last Patient Last Visit where the final study subject is examined or receives an intervention for the purpose of data collection pertaining to primary and secondary outcome measures and adverse events, regardless of whether the study concluded according to the pre-specified protocol or was terminated. [Section 6.2](#) details the events that would lead to study suspension or premature termination by Corbus.

## 8. STUDY ASSESSMENTS AND PROCEDURES

Planned time points for all study procedures are provided in the schedule of assessments (SOA) in [Section 7.1](#).

### 8.1. Efficacy Assessments

#### 8.1.1. Training in Efficacy Assessments

Physicians or a designated health care professional will be trained in the performance of all physician assessments of efficacy. It is expected that the same individual will perform the physician assessments of efficacy at all visits, except in uncommon circumstances. There is a 2-week window for each study visit starting with Visit 2 to facilitate scheduling to allow for consistency in the assessor of efficacy outcomes. In general, it is preferred that a given visit be slightly delayed to allow for the same individual to assess efficacy outcomes throughout the study, rather than have a different assessor. This is particularly important for visits when TIS is being evaluated (see [Table 3](#) and [Table 4](#)).

Subjects will be trained in the questionnaires used to assess patient-reported efficacy outcomes. This training will be done at Screening, so subjects can become familiar with the instruments prior to establishing Baseline values at Visit 1. Starting with Visit 1, it is expected that patient-reported efficacy assessments should be completed independent of input from study staff.

Study staff will be trained in the performance of spirometry using centrally supplied equipment. It is preferred that the same individual perform spirometry at each visit for a given subject, as practicable.

All efficacy assessments for the TIS will be calculated centrally.

#### 8.1.2. Total Improvement Score (TIS)

Efficacy will be assessed using the 2016 ACR/EULAR Myositis Response Criteria Total Improvement Score, comparing the change from Baseline between lenabasum and placebo groups.

Myositis response criteria were developed for both juvenile and adult populations and are based on a 0 – 100 scale. Six core measures are used to calculate the TIS ([Aggarwal et al., 2017](#)). Higher scores indicate better improvement in myositis.

The six measures that comprise the TIS are summarized below:

- **Physician Global Activity (MDGA):** An assessment of overall global disease activity by the physician will be done using a 10-cm VAS. The Physician Assessments should ideally be done by the same investigator. The physician should refer to subject's MDGA score from the previous visit to ensure consistency in rating.
- **Patient Global Activity (PtGA):** An assessment of overall global disease activity by the patient will be done using a 10-cm VAS.
- **Manual Muscle Testing-8 (MMT-8):** For MMT assessment, a MMT that assesses strength in 8 muscle groups (MMT-8) will be used. Strength in 8 muscle groups will be assessed on a 0 – 10 point scale (see [Table 5](#)) and recorded. Strength in the following 7

muscle groups will be assessed bilaterally: deltoid, biceps, wrist extensors, gluteus maximus, gluteus medius, quadriceps, ankle dorsiflexors. In addition, strength in the neck flexors will be assessed.

**Table 5: Description of Rating of Muscle Strength in Individual Muscle Groups for MMT-8 Scoring**

Rating (lower score is weaker, higher score is stronger)	Description
0	No contraction of muscle is felt
1	Moves through partial range of motion in the horizontal plane
2	Moves through completion of range of motion in the horizontal plane
3	Moves through completion of range of motion against resistance in the horizontal plane or holds against pressure or moves through partial range of motion in an antigravity position
4	Gradual release from test position in an antigravity position
5	Holds test position (no added pressure) in an antigravity position
6	Holds test position against slight pressure in an antigravity position
7	Holds test position against slight to moderate pressure in an antigravity position
8	Holds test position against moderate pressure in an antigravity position
9	Holds test position against moderate to strong pressure in an antigravity position
10	Holds test position against strong pressure in an antigravity position

- **Health Assessment Questionnaire-Disability Index (HAQ-DI):** The HAQ-DI provides a patient-reported assessment of functional disability ([Aggarwal et al, 2017](#)) and includes 8 sections: dressing, arising, eating, walking, hygiene, reach, grip, and activities. There are 2 to 3 questions for each section; the recall period is 1 week. Scoring within each section is from 0 (without any difficulty) to 3 (unable to do). Scores are adjusted for use of aides, devices, or help from others. For the HAQ-DI, the score of each individual section is the highest score in that section. A higher total score indicates more functional disability.

- **Extramuscular Global Activity (EMGA):** The EMGA encompasses an overall evaluation for the disease activity in all the extramuscular organ systems and excludes muscle disease activity. EMGA will be assessed by drawing a vertical mark on a 0-10cm VAS scale. Anchored at each end of the 10-cm VAS are the descriptors “absent” and “maximum.”
- **Muscle Enzymes:** The serum activities of the following muscle-associated enzymes will be assessed: the transaminases (ALT, AST), LDH, CK, and aldolase. The AST, ALT and LDH values will be done as part of the metabolic panel and CK and aldolase will be measured as additional muscle enzymes. The most abnormal (by percentage) muscle enzyme at Baseline will be used in calculations of TIS. All muscle enzymes will be done at a central laboratory.

Please see [Appendix 6](#) for algorithm to calculate TIS ([Aggarwal et al, 2017](#)).

Because TIS is a composite score, absolute values and change from Baseline in each core set measure will be presented to support the primary efficacy endpoint.

### **8.1.3. Definition of Improvement (DOI)**

The definition of improvement (DOI) (Oddis et al, 2013) is  $\geq 20\%$  improvement in 3 of any 6 core set measures (same as used to determine the TIS), with no more than 2 core set measures worsening by  $\geq 25\%$ . For DOI to be achieved, the MMT-8 cannot worsen by  $\geq 25\%$ . For improvement in muscle enzymes to contribute to DOI, the muscle enzyme value must be greater than the upper limit of normal at Baseline. For worsening in muscle enzymes to contribute to the DOI, the muscle enzyme value must be greater than the upper limit of normal at the time of worsening.

### **8.1.4. Cutaneous Dermatomyositis Disease Area and Severity Index (CDASI) Score**

CDASI is a validated outcome measure that systematically quantifies cutaneous DM disease activity and damage ([Klein et al, 2007](#); [Yassaei et al, 2010](#)). In the CDASI, DM skin disease activity is evaluated based on the physician's/qualified health personnel evaluation of erythema, scale, and erosion or ulceration at fifteen anatomic locations as well as alopecia, Gottron's sign or papules on the hands, and periungual changes. Damage is evaluated based on poikiloderma and calcinosis at fifteen anatomic locations as well as Gottron's sign.

### **8.1.5. Investigator Global Assessment (IGA) scale of skin activity**

The IGA is a 5-point scale to evaluate overall skin disease by the investigator. Skin will be assessed as clear, almost clear, mild, moderate, or severe based on the overall description of each category as provided in [Appendix 2](#).

### **8.1.6. Short-Form-36 (SF-36)**

The Short Form 36-question health survey (SF-36) is a widely used tool that assesses the global medical quality of life, functional health, and well-being of general and specific populations. The SF-36 is comprised of 36 questions that cover the following 8 health concepts: physical functioning, bodily pain, role limitations due to physical health problems, role limitations due to

personal or emotional problems, emotional well-being, social functioning, energy/fatigue, and general health perceptions.

### **8.1.7. Corticosteroid Dose**

Corticosteroids are commonly prescribed for the treatment of signs and symptoms of DM. Corticosteroid dose will be recorded as a concomitant medication, with start and stop dates. Change from Baseline in corticosteroid dose will be compared between the lenabasum 20 mg BID and placebo groups and the lenabasum 5 mg BID and placebo groups (see [Section 9.4.3](#)).

### **8.1.8. Forced Vital Capacity**

Spirometry to measure FVC (actual and % predicted values) will be done using equipment supplied by the Sponsor. Study staff will be trained in the proper use of the spirometry equipment. As possible, the same operator should record spirometry for a given subject. FVC values will be measured and calculated in compliance with American Thoracic Society standards for spirometry ([Miller et al, 2005](#)). Hankinson's reference values ([Hankinson et al, 2010](#)) will be used to determine FVC percent prediction with additional correction for Asian subjects.

### **8.1.9. Physician Global Activity (MDGA) – Likert Scale**

A second assessment of overall global disease activity by the physician will be done with a 5-point Likert scale that uses the following scoring: 0 = None; 1 = Mild; 2 = Moderate; 3 = Severe; 4 = Extremely severe.

### **8.1.10. Patient Improvement Questionnaire for Physicians**

A brief questionnaire (see [Appendix 3](#)) will be administered that will determine overall improvement with treatment in the investigator's judgment.

### **8.1.11. Functional Assessment of Chronic Illness Therapy (FACIT)-Fatigue score**

The FACIT-F score is a 13-item patient-reported questionnaire that assesses tiredness, weakness, and difficulty conducting everyday activities due to fatigue in the last 7 days ([Butt et al, 2013](#)). Items are scored on a 5-point scale (0 = not at all, 4 = very much). All items except item 7 and 8 are reverse-scored before item scores are summed to obtain a total score (range 0-52). A higher score indicates less fatigue. The FACIT fatigue tool has been previously validated in a study by [Chandran et al, 2007](#).

### **8.1.12. 5-Dimension (5-D) Itch Score**

The 5-D Itch scale is a validated patient-reported assessment of itch in skin diseases ([Elman et al, 2010](#)). It is a brief, multidimensional questionnaire with five dimensions of itch - degree, duration, direction, disability and distribution. The period of recall is 2 weeks. Single-item domain scores range from 1-5. The scores of each domain are summed to obtain a total 5-D Itch score. Total 5-D Itch scores can range between 5 (no itch) and 25 (most severe itch). A higher score indicates worse itch.

### **8.1.13. National Institutes of Health Patient-Reported Outcomes Measurement Information System (PROMIS)-29 Short Form**

The PROMIS-29 Short Form (Version 2.0) will be used to assess patient-reported state of health. The National Institutes of Health established PROMIS ([www.nihpromis.org](http://www.nihpromis.org)) to create a standardized and uniformly scored set of patient-reported-outcomes instruments. The PROMIS network developed item (question) banks and Short Forms in more than 20 health domains as well as a set of global health items and 29-, 43-, and 57-item profile measures. To create a brief, practical-yet-inclusive short profile, a consensus-building process was used to identify 7 of these 20 domains to produce the PROMIS-29. The seven domains specifically relate to physical, mental and social health and cover the most relevant areas of self-reported health for the greatest majority of people with chronic illness: pain interference, fatigue, depression, anxiety, sleep disturbance, physical function and social role. The PROMIS-29 includes four items each from these seven core PROMIS domains as well as one 11-point rating scale for pain intensity. Norm-based scores have been calculated for each domain, such that a score of 50 represents the mean of the general population (standard deviation = 10). High scores represent more of the domain being measured. Thus, on symptom-oriented domains of PROMIS-29 (anxiety, depression, fatigue, pain interference, and sleep disturbance), higher scores represent worse symptomatology. On the function-oriented domains (physical functioning and social role) higher scores represent better functioning.

### **8.1.14. Patient Visual Analog Scale (VAS) scores of Pain**

All subjects will record their overall pain by drawing a vertical mark on a 0-10cm VAS scale. The 10-cm VAS is anchored at each end with descriptors of “no pain” (0) and “pain as bad as it could be” (10) anchored at each end.

### **8.1.15. Skindex-29+3**

The Skindex-29 ([Chren 1997](#)) is a validated, 29-item skin-specific quality of life questionnaire used to calculate three subscales: symptoms, emotions and functioning. The Skindex-29+3 includes the addition of a fourth subscale, consisting of three questions, to assess photosensitivity and alopecia ([Klein 2011](#)). Each question and subscale range from 0-100 points, with higher scores indicating worse quality of life.

### **8.1.16. European Quality of Life 5-domain (EQ-5D) questionnaire score**

The EQ-5D is a standardized measure of health status intended to provide a simple and generic measure of health and is comprised of 5 dimensions - anxiety/depression, mobility, self-care, usual activities, and pain/discomfort.

### **8.1.17. Patient Improvement Questionnaire for Subjects**

A brief questionnaire (see [Appendix 4](#)) will be administered to determine overall improvement with treatment from study start (Yes or No), as per the subject’s perception. Subjects who answer “Yes” will be asked to rate whether the degree of improvement was slight, moderate, or marked. The MID for TIS, HAQ-DI score, and CDASI activity score in DM will be calculated separately as the mean score of each of these outcomes in all subjects who answered that they had slight improvement at that given timepoint (16 Weeks, 26 Weeks, and 52 Weeks).

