### Objectives and Endpoints:

Primary Objective	Primary Efficacy Endpoint
To evaluate the efficacy of lenabasum compared to placebo in subjects with dermatomyositis (DM)	
Total Improvement Score (TIS) by the 2016 American College of Rheumatology (ACR)/European League Against Rheumatism (EULAR) Myositis Response Criteria at Week 28
 
The TIS is comprised of 6 core set measures and absolute value and change from baseline in each core set measure will be presented to support the composite TIS:
 

1. Physician global activity (MDGA)

2. Patient global activity (PtGA)

3. Manual Muscle Testing (MMT)

4. Health Assessment Questionnaire (HAQ)

5. Muscle enzymes

6. Extramuscular global activity (EMGA)

 
A MMT that assesses strength in 8 muscle groups (MMT-8) will be used in this study.

Secondary Efficacy Endpoints	
	
The following endpoints will be compared in lenabasum 20 mg BID and placebo cohorts and lenabasum 5 mg BID and placebo cohorts at Week 28, unless otherwise specified. All outcomes involving continuous variables will be assessed as absolute values and, if relevant, change from Baseline. All categorical variables will be assessed as number and proportion of subjects in each category:
 

1. Subjects who achieve Definition of Improvement (DOI), defined as <math>\geq 3</math> of 6 core set measures improved by <math>\geq 20\%</math> (relative to Baseline) with no more than 2 core set measures worsening by <math>\geq 25\%</math> (MMT-8 may not decrease by <math>\geq 25\%</math> from baseline)

2. Subjects who improve by at least one category on the Investigator Global Assessment (IGA) scale of skin activity

3. Subjects who achieve TIS <math>\geq 40</math> (at least moderate improvement)

	

4. TIS in subjects receiving any immunosuppressant medication for > 1 year at Baseline

5. TIS at Visit 10 (Week 52)

6. Cutaneous Dermatomyositis Disease Area and Severity Index (CDASI) activity score

7. TIS (lenabasum 5 mg compared to placebo cohorts only)

	Tertiary Efficacy Endpoints
	
These endpoints will be assessed at all visits at which they are measured, if not already included as the primary or secondary efficacy endpoints. Additional tertiary efficacy endpoints may be included in the Statistical Analysis Plan (SAP).

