	
Change from Baseline compared to placebo in physician or laboratory assessments:
 

1. Forced vital capacity (FVC) absolute change in mL and percent predicted

2. CDASI damage score

3. MDGA (Likert Scale)

4. Corticosteroid dose

 
Change from Baseline compared to placebo in patient reported outcomes:
 

1. Functional Assessment of Chronic Illness Therapy (FACIT)-Fatigue Score

2. 5-D Itch Score

3. National Institutes of Health Patient-Reported Outcomes Measurement Information System (PROMIS)-29 Short Form domain scores

4. Patient Visual Analog Scale (VAS) scores of Pain

5. Skindex-29+3

6. European Quality of Life 5-domain (EQ-5D) questionnaire score

7. SF-36 domain scores

 
Proportion of subjects:
 

1. Achieving a CDASI activity score of <math>\leq 14</math>

2. Achieving clear or almost clear skin on the IGA scale of skin activity

3. Achieving a TIS of <math>\geq 20</math>, <math>\geq 40</math>, and <math>\geq 60</math>

	

4. Achieving a reduction in dose of any immunosuppressive medication (including corticosteroid) for > 28 days, among subjects receiving immunosuppressive medications at Baseline

5. Requiring an increase in dose of any immunosuppressive medication (including corticosteroids), or rescue immunosuppression for > 28 days

 
Subset analyses of outcomes above by Baseline characteristics:
 

1. TIS by: MMT-8 score and other core set measures as continuous variables

2. TIS and core set measures and secondary outcomes by: age (continuous variable); geographic region (US, ex-US); any non-corticosteroid immunosuppressive treatment (yes, no); dose of oral prednisone or equivalent

 
Minimal Important Difference (MID):
 

1. Determine MID in TIS, HAQ-DI and CDASI in DM

2. Subset analysis to determine proportion of subjects that achieve MID in TIS, HAQ-DI and CDASI

--	--

Secondary Objective	Safety Endpoints

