## 4. STUDY POPULATION

### 4.1. Inclusion Criteria

Subjects must meet ALL of the following criteria to be eligible for the study:

1. Able to understand and voluntarily sign the informed consent
2. Male or female  $\geq 18$  years of age at the time of signing the informed consent
3. Fulfill one of the following criteria for DM:
  - a. Bohan and Peter's criteria for probable or definite DM ([Bohan and Peter, 1975a](#); [Bohan and Peter 1975b](#))
  - b. ACR/EULAR criteria ([Lundberg et al, 2017](#))
4. Subject has active DM as determined by the investigator
5. Disease activity/severity fulfils one of the following three criteria:
  - i. MDGA  $\geq 3$  cm (0-10 cm scale) and MMT-8 score  $\leq 142$  (out of 150 total possible)
  - ii. Sum of MDGA, PtGA and EMGA VAS scores is  $\geq 10$  cm (all scales individually on 0-10 cm scale)
  - iii. MDGA  $\geq 3$  cm and CDASI activity score of  $>14$
6. Stable doses of immunosuppressive medications for DM as defined by:
  - a. Unchanged dose of oral corticosteroids  $\leq 20$  mg per day prednisone or equivalent for  $\geq 4$  weeks before Visit 1
  - b. Unchanged dose of immunosuppressive medications other than oral corticosteroids for  $\geq 8$  weeks before Screening
7. Willing to not start or stop any immunosuppressive medications for DM from Screening through end of study, unless a change is part of the protocol or considered in the subject's best medical interest by the site investigator or another physician who has primary responsibility for treating the subject's DM.
8. Willing to not use any cannabinoids, including recreational marijuana, medical marijuana and other prescription cannabinoids from Screening through end of study.
9. Able to adhere to the study visit schedule and other protocol requirements and follow study restrictions.
10. Women of childbearing potential (WOCBP) must not be pregnant or breastfeeding and they or their male sexual partner must be using at least one acceptable method of contraception (see [Appendix 1](#)) for at least 4 weeks before Visit 1 and be willing to continue its use for at least 4 weeks after discontinuation of study product.

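### Section 8.1.17 sets the MID for HAQ-DI and CDASI activity as a mean score in slight improvers, which is a disease level and not a difference

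*Protocol*

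**What the plan says.** Section 8.1.17 describes a questionnaire in which subjects say whether they have improved since the start of the study and, if so, whether slightly, moderately or markedly. It then fixes how the MID is computed. For TIS, HAQ-DI and CDASI activity alike, it is "calculated separately as the mean score of each of these outcomes in all subjects who answered that they had slight improvement", at "16 Weeks, 26 Weeks, and 52 Weeks". The sentence mentions neither Baseline nor change.

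The synopsis lists two tertiary MID items: to determine the MID in the three measures, and then "Subset analysis to determine proportion of subjects that achieve MID in TIS, HAQ-DI and CDASI".

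The protocol describes the three measures differently:

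- TIS (Section 8.1.2): "Higher scores indicate better improvement in myositis".
- HAQ-DI (Section 8.1.2): "A higher total score indicates more functional disability".
- CDASI (Section 8.1.4): "CDASI is a validated outcome measure that systematically quantifies cutaneous DM disease activity and damage".

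Elsewhere the protocol keeps level and change apart. For the secondary endpoints the synopsis states: "All outcomes involving continuous variables will be assessed as absolute values and, if relevant, change from Baseline".

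**The concern.** One formula is applied to two kinds of measure. TIS is built from changes since Baseline, so its mean in slight improvers is a sensible MID. HAQ-DI and CDASI activity describe the subject's state at the visit. Their mean in slight improvers says how ill those subjects still are, not how much they have changed.

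The MID is then to serve as a threshold that subjects achieve. If the threshold is a level, whether a subject passes depends largely on where that subject started. Baseline severity will vary by design. In Section 4.1, "Disease activity/severity fulfils one of the following three criteria", and only one of those three routes requires a minimum CDASI activity score (above 14). The HAQ-DI and CDASI figures would then reflect the case mix of this trial's slight improvers, and the named aim of determining an MID for those measures in dermatomyositis would not be met.

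**Working it through.** The protocol states no numerical MID, so there is no figure to reproduce. The check is algebraic.

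**Identity.** Among slight improvers at a given visit, let B be the mean Baseline score and d the mean improvement (a fall in score, for both HAQ-DI and CDASI).

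- Mean score at the visit = B − d. This is what Section 8.1.17 returns.
- Mean improvement from Baseline = d. This is what an MID should be.
- Ratio of the two = (B − d)/d.

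The literal figure rises one-for-one with B and falls one-for-one as d grows. Neither fact depends on the values chosen.

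**Illustration.** The protocol gives neither B nor d, so every value below is assumed. Each cell shows B − d, with the ratio to d in brackets.

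HAQ-DI:

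| B | d = 0.1 | d = 0.2 | d = 0.3 |
|---|---|---|---|
| 0.6 | 0.5 (5.0) | 0.4 (2.0) | 0.3 (1.0) |
| 0.9 | 0.8 (8.0) | 0.7 (3.5) | 0.6 (2.0) |
| 1.2 | 1.1 (11.0) | 1.0 (5.0) | 0.9 (3.0) |

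CDASI activity:

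| B | d = 3 | d = 5 | d = 8 |
|---|---|---|---|
| 15 | 12 (4.0) | 10 (2.0) | 7 (0.9) |
| 25 | 22 (7.3) | 20 (4.0) | 17 (2.1) |
| 35 | 32 (10.7) | 30 (6.0) | 27 (3.4) |

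**Case mix alone.** Hold the CDASI improvement at 5 points. Suppose skin-active slight improvers start at 25 and the others at 8.

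- 30% skin-active: B = 0.30 × 25 + 0.70 × 8 = 13.1, so the rule gives 13.1 − 5 = 8.1.
- 80% skin-active: B = 0.80 × 25 + 0.20 × 8 = 21.6, so the rule gives 21.6 − 5 = 16.6.

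The stated MID doubles although nobody's improvement has changed.

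**As a threshold.** Take B = 25 and d = 5, so the rule gives 20. There are two ways to use it:

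- As a level to reach: a subject who starts and stays at 15 passes without improving, while one who falls from 35 to 22, a gain of 13 points, fails.
- As an amount of improvement: a subject who starts at 15 cannot pass at all.

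**Timepoints.** Sections 7.2.1.6, 7.2.1.7 and 7.2.1.9 give the questionnaire at Weeks 16, 28 and 52. Week 26 falls outside the windows of the visits on either side of it: 22 ± 1 (Weeks 21 to 23) and 28 ± 1 (Weeks 27 to 29).

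**The case against.** The strongest reply is that this is loose drafting and that change was meant. MID stands for a difference. The questionnaire asks about improvement since study start. The synopsis and Section 9.4.3 say that continuous secondary and tertiary variables are modelled with change from Baseline as the dependent variable. Section 9.4.4, on the tertiary analyses, is a bare heading in the public text, and Section 2 leaves endpoints to be finalised in the SAP, which was not available here. The correct computation may be set out there.

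Much of this is fair as to intent, and what would actually be programmed cannot be known from the protocol. But Section 8.1.17 is not silent: it states a formula. The modelling sentence governs the repeated-measures analysis and does not redefine a descriptive mean in a subgroup chosen by questionnaire answer. The protocol also uses the CDASI activity score as a level, above 14 for entry and at most 14 as a response target in the synopsis. Nothing visible says that score means change here.

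Two further points stand:

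- The illustrations rest wholly on assumed values and add nothing to the identity beyond scale. The case-mix example also assumes the same 5-point gain from a Baseline of 8 (5/8, about 63%) as from 25 (5/25, 20%), which no document supports.
- A mean change can itself depend on Baseline, since a subject at CDASI 8 cannot improve by more than 8 points. The correction gives the right kind of quantity; it does not guarantee that the value carries over to other populations.

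**Conclusion.** The concern holds on the text as written. For HAQ-DI and CDASI activity, the rule in Section 8.1.17 returns mean Baseline minus mean improvement, which is not a minimal important difference. For TIS the rule is sound.

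The error cannot be sized from the protocol. Over the assumed ranges, the rule returns 1 to 11 times the improvement for HAQ-DI and 0.9 to 10.7 times for CDASI, so it may agree by chance or miss widely. That it is the wrong quantity follows from the algebra and needs none of these assumptions.

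The reach is limited to the tertiary MID items for these two measures. They lie outside the testing hierarchy in Section 9.4.1.2, so the primary and secondary results, the type I error and the power are untouched. The correction should still be made before unblinding, so that the definition is not chosen with the results in view. The Week 26 reference is a separate, editorial slip.

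**What to change.** Reword Section 8.1.17 along these lines: the MID is the mean change from Baseline in HAQ-DI and in CDASI activity score, and the mean TIS, among subjects reporting slight improvement at Weeks 16, 28 and 52. Add that a subject achieves the MID by improving at least that much, with improvement meaning a decrease for HAQ-DI and CDASI activity. The reference to 26 weeks becomes 28 weeks.

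Carry the same wording into the SAP. Baseline is already defined in Section 9.4.1, and the scores and questionnaire answers are already collected at these visits. The cost is one or two sentences, with no new data, no added visits and no change to the sample size.
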